2.7.2.1 Week 24 analysis

Responder analysis

For the responder analysis, a logistic regression model will be performed using the percent decrease in body weight from BL at Week 24 $\geq 5\%$ or $\geq 10\%$ (yes/no) as a response variable, treatment, glycemic stratification factor and region as fixed factors and BL body weight as a covariate, respectively. The Week 24 missing values will be imputed using the multiple imputation method as described in Section 2.5.3. In order to account for the imputation uncertainty, this logistic regression model will be repeated for each imputed dataset, which results in a set of estimated odds ratio and associated 95% confidence intervals for each LIK066 dose vs placebo contrast, for all dose groups and regimens. Rubin's rule will be used to combine the multiple sets of odds ratios and 95% confidence intervals to a single set of odds ratio and its 95% confidence interval of an LIK066 dose vs placebo. Similar analysis by glycemic status stratification factor will be performed to assess the responder rate for each of the subgroups (normoglycemic subjects, dysglycemic subjects and subjects with T2DM).

In addition, subjects meeting the predefined response criteria (percent decrease in body weight from BL at Week 24 $\geq 5\%$ or $\geq 10\%$) will be summarized by treatment for all subjects and by glycemic stratification factor. A Cochran-Mantel-Haenszel-test will be performed to compare each qd or bid dose to the common placebo.

Dose-response relationship by glycemic stratification factor

For the dose-response relationship in normoglycemic subjects, dysglycemic subjects and subjects with T2DM, the dose-response modeling with the same candidate model sets for the

primary variable as described in Section 2.5.2 will be performed on percent change of body weight from BL at Week 24 for these three subsets of subjects separately.

Summary statistics for body weight will be presented by visit and treatment for observed and imputed values by glycemic stratification factor. Figures will be produced to visually show the raw mean percent changes and the adjusted mean percent changes from the dose response modeling by visit over 24 weeks of Epoch 3 for each treatment group by glycemic stratification factor as well.

Other secondary endpoints

For changes from BL at Week 24 in HbA1c, FPG, SBP, DBP, waist circumference and 24-h UGE, a repeated measure ANCOVA model with treatment, visit, stratification factor (normoglycemic, dysglycemic, and T2DM), pooled center or region, and treatment by visit interaction as fixed-effect factors, BL and BL by visit interaction as covariates, and a common unstructured covariance matrix among visits between treatments will be performed separately for each variable. The adjusted mean changes at Week 24 within each treatment, the differences in mean changes at Week 24 between the LIK066 and placebo treatments, and their 95 % confidence intervals obtained from the above model will be presented. The analysis is based on likelihood method with an assumption of MAR for missing data.

The same repeated measure ANCOVA model will be fitted for each stratum (normoglycemic, dysglycemic, and T2DM) as well, and the adjusted mean changes at Week 24 within each treatment, the differences in mean changes at Week 24 between the LIK066 and placebo treatments for each stratum, and their 95% confidence intervals obtained from the above models will be presented by strata for each efficacy endpoint.

Similar repeated measure ANCOVA models will be performed for percent changes of lipid parameters and \log_{10} transformed hsCRP from BL at Week 24.

Summaries of absolute values and change from BL by treatment group and visit will be presented for all secondary efficacy variables for all subjects and by strata. Figures will be produced to visually show the raw mean changes by visit over 24 weeks of Epoch 3 for each treatment group, for overall and by strata separately.

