### **5.2 Treatment arms**

All subjects entering Epoch 2 (run-in) will receive placebo.

At Visit 201 (randomization), subjects eligible for randomization will be assigned 1:1:1:2:1:1:1:2:2 to one of the following treatment arms in Epoch 3 (see [Section 3.1.2](#)):

- 2.5 mg qd LIK066 (approx. 36 subjects).
- 10 mg qd LIK066 (approx. 36 subjects).
- 50 mg qd LIK066 (approx. 36 subjects).
- 150 mg qd LIK066 (approx. 72 subjects).
- 2.5 mg bid LIK066 (approx. 36 subjects).
- 5 mg bid LIK066 (approx. 36 subjects).
- 25 mg bid LIK066 (approx. 36 subjects).
- 50 mg bid LIK066 (approx. 72 subjects).

- Placebo (approx. 72 subjects).

At the end of Epoch 3, subjects from each of the four qd arms will enter Epoch 4 and will receive 25 mg qd LIK066. Subjects from each of the four bid arms in Epoch 3 will receive 35 mg qd LIK066 in Epoch 4.

The subjects from the Epoch 3 placebo arm will receive placebo or 25 mg qd LIK066 in Epoch 4 in a 1:1 fashion (see [Section 3.1.3](#)).

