### **5.3 Treatment assignment and randomization**

At Visit 201 (randomization), all eligible subjects will be randomized via Interactive Response Technology (IRT) to one of the treatment arms for Epoch 3, and within that treatment arm to one of the regimens in Epoch 4. The investigator or his/her delegate will contact the IRT system after confirming that the subject fulfills all the inclusion/exclusion criteria (see [Section 4](#)). The IRT system will assign a randomization number to the subject, which will be used to link the subject to a treatment arm and will specify a unique medication number for the first package of study drug to be dispensed to the subject. The randomization number will not be communicated to the user.

The randomization numbers will be generated using the following procedure to ensure that treatment assignment is unbiased and concealed from subjects and investigator staff. A subject randomization list will be produced by the IRT provider using a validated system that automates the random assignment of subject numbers to randomization numbers. These randomization numbers are linked to the different treatment arms, which in turn are linked to medication numbers. A separate medication list will be produced by or under the responsibility of Novartis drug supply management using a validated system that automates the random assignment of medication numbers to packs containing the investigational drug(s).

Randomization will be stratified into (see [Section 3.1.2](#)):

- Normoglycemic.
- T2DM.
- Dysglycemic.

Efforts will be made by close monitoring of the enrollment through the IRT system to ensure each of the three stratification sub-groups with at least 30 % of total subjects enrolled in the study.

The randomization scheme for subjects will be reviewed and approved by a member of the Novartis randomization office.

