2.14 Interim analysis

Not applicable.

3 Sample size calculation

The study planned to randomize approximately 432 subjects in total, allocated in the ratio of 1:1:1:1:1:2:1:1:1:2 to the following 10 Epoch 3/Epoch 4 treatment groups:

1. placebo/placebo
2. placebo/LIK066 25 mg qd
3. LIK066 2.5 mg qd/25 mg qd
4. LIK066 10 mg qd/25 mg qd
5. LIK066 50 mg qd/25 mg qd
6. LIK066 150 mg qd/25 mg qd
7. LIK066 2.5 mg bid/35 mg qd
8. LIK066 5 mg bid/35 mg qd
9. LIK066 25 mg bid/35 mg qd
10. LIK066 50 mg bid/35 mg qd

This randomization scheme implies that the Epoch 3 treatment and Epoch 4 treatment for a specific subject is determined simultaneously at randomization visit. The randomization will be stratified by subjects' glycemic status at screening: normoglycemic, dysglycemic and T2DM.

As the dose-response assessment is conducted in qd and bid regimens separately (while an overall family-wise type I error is controlled at a one-sided significance level of 2.5 %), power calculation was done for testing dose-response signal by regimen as well. Table 3-1 summarizes the average power and the lowest power across the candidate dose response shapes in Figure 2-1 by regimen, under different scenarios with the assumptions on effect size of body weight loss (percent change from BL) for the dose of maximum effect, and the related standard deviations.

Note that a dose-response signal is detected (ie the primary objective is met) as long as either of the dose-response signals for the two regimens is detected. Therefore, the overall study power is at least the maximum of the powers between two regimens for each scenario considered.

Table 3-1 Power for detecting a significant dose response signal*

Dose regimen	Effect size for best dose	SD	Average power**	Minimum power†
Qd	5 %	5.5 %	99.99 %	99.98 %
	5 %	6.5 %	99.71 %	99.57 %
	6 %	5.5 %	99.99 %	99.99 %
	6 %	6.5 %	99.99 %	99.98 %
Bid	5 %	5.5 %	99.16 %	95.84 %
	5 %	6.5 %	96.50 %	86.79 %
	6 %	5.5 %	99.90 %	99.43 %
	6 %	6.5 %	99.28 %	96.36 %

Dose regimen	Effect size for best dose	SD	Average power**	Minimum power†
--------------	---------------------------	----	-----------------	----------------

* Assumes 432 subjects in LIK066 and placebo arms with effective sample size of 367 subjects due to an effect of missing data equivalent to 15 % fewer subjects. Calculations were performed using the DoseFinding package in R.

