† Power for a significant dose-response contrast test across all scenarios within each regimen in Table 3-1. The candidate model #5 in bid regimen has the lowest power.

It was assumed that the effect of losses to follow-up is equivalent to effectively having 15 % fewer subjects than randomized, even if the multiple imputation approach used to handle missing values should be able to recover some information for such subjects.

4 Change to protocol specified analyses

In protocol section 9.5.1.1 change from BL at Week 24 in hsCRP was listed as one of the secondary efficacy variables, and this has been modified to percent change from BL at Week 24 in hsCRP in \log_{10} transformation in the SAP.

5 Appendix

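### The by-stratum logistic models for the 10% responder threshold are likely to meet an arm with no responders, which leaves the affected pooled odds ratios meaningless, and the SAP names no fallback

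*SAP*

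**What the plan says.** SAP 2.7.2.1 (Responder analysis) regresses response, defined as at least 5% or at least 10% weight loss at Week 24, on treatment (nine arms), glycemic stratum, region and baseline weight. The model is fitted to each imputed dataset, and the odds ratios and intervals are combined by Rubin's rule. The SAP then states: "Similar analysis by glycemic status stratification factor will be performed to assess the responder rate for each of the subgroups". Protocol 9.5.1.1 plans the same.

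The next paragraph of SAP 2.7.2.1 adds a summary of responders by treatment and by glycemic stratum, and a Cochran-Mantel-Haenszel test.

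On cell sizes, Protocol 5.2 gives "2.5 mg qd LIK066 (approx. 36 subjects") for a small active arm and "Placebo (approx. 72 subjects") for the control. The 150 mg qd and 50 mg bid arms also have about 72. Protocol 5.3 aims to "ensure each of the three stratification sub-groups with at least 30 % of total subjects enrolled in the study".

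Neither document gives an expected responder rate. Neither names a penalised or exact method, a minimum count, or a rule for an arm without responders. The SAP history drops subgroup analyses for the end-of-study analysis only, so the Week 24 by-stratum analysis stands.

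**The concern.** An ordinary logistic regression, which is the natural reading of the SAP, has no finite estimate for an arm in which nobody responds. With about a dozen subjects in each of six arms per stratum, and a threshold as demanding as 10%, such arms can be expected.

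Multiple imputation makes this worse. A cell may be empty in some imputed datasets and not in others, so Rubin's rule would average stable estimates with values set by the software's stopping rule.

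At stake are the by-stratum 10% odds ratios, one of the outputs serving secondary objective 1. With no rule stated in advance, any remedy would be chosen after the data are seen.

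**Working it through.** **Cell sizes.** SAP Section 3 allocates 432 subjects in 12 units ("allocated in the ratio of 1:1:1:1:1:2:1:1:1:2 to the following 10 Epoch 3/Epoch 4 treatment groups"): 432/12 = 36 per small arm and 2 × 36 = 72 for placebo and each top dose. The effective size also reproduces: 432 × 0.85 = 367.2, against the stated 367. With three strata of at least 30% each, no stratum can exceed 40%. Small arms then have 36 × 0.30 = 10.8 to 36 × 0.40 = 14.4 subjects per stratum, and the large arms 21.6 to 28.8. Equal strata give 12 and 24, used below.

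**Formulas.** Responder rate p = Φ((−10 − mean)/SD). P(arm empty) = (1 − p)^n. P(at least one of nine arms empty) = 1 − Π(1 − P(arm empty)). For three strata, 1 − (1 − P)³.

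**Inputs from the plan.** SD 5.5% or 6.5% and best-dose effect 5% or 6% (SAP Table 3-1); Emax shapes with ED50 5 or 50 mg total daily dose (SAP Table 2-3, models 1 and 2).

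**Assumptions.** Placebo mean change 0, −1, −2 or −3%; normally distributed percent change; the full effect reached at 150 mg/day for qd and at 100 mg/day for bid; the same rates in every stratum.

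**One case worked through** (effect 5%, SD 6.5%, ED50 50 mg, placebo mean −2%):
- 2.5 mg qd: share of the best-dose effect = (2.5/52.5)/(150/200) = 0.063, so mean = −2 − 5 × 0.063 = −2.32. p = Φ(−7.68/6.5) = 0.119, and (1 − 0.119)^12 = 0.22.
- Placebo: p = Φ(−8/6.5) = 0.109, and (1 − 0.109)^24 = 0.06.
- The other arms, from low to high dose: qd 0.15, 0.04, 0.00; bid 0.19, 0.14, 0.03, 0.00.
- At least one empty arm: 0.60 per stratum; 1 − 0.40³ = 0.94 over three strata.

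**All 32 scenarios** (per stratum; ranges over effect and SD):

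| Placebo mean | Any arm empty, ED50 5 mg | Any arm empty, ED50 50 mg | Placebo empty (SD 5.5 / 6.5) |
|---|---|---|---|
| 0% | 0.60–0.90 | 0.89–0.99 | 0.43 / 0.22 |
| −1% | 0.40–0.73 | 0.75–0.94 | 0.29 / 0.12 |
| −2% | 0.23–0.50 | 0.56–0.82 | 0.16 / 0.06 |
| −3% | 0.11–0.27 | 0.36–0.62 | 0.08 / 0.03 |

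The range is 0.11–0.99 per stratum, and 0.50 or more (to two decimals) in 21 of 32 scenarios. Over three strata it is 0.29–1.00, and above 0.50 in 30 of 32. The expected number of empty cells among the 18 small ones is 0.3 to 7.9.

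**Without a dose-response assumption.** A 12-subject arm is empty with probability 0.54 at a true rate of 5%, 0.28 at 10%, 0.14 at 15% and 0.07 at 20%.

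**What the fit does.** In one simulated stratum with an empty 2.5 mg qd arm, that arm's log odds ratio was −8.1 (SE 28) after 8 Newton-Raphson iterations, −12.1 (SE 205) after 12 and −20.1 (SE 11,205) after 20. The other arms' estimates did not move.

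**Imputation.** Take 15% missing, 20 imputations (assumed) and a 12-subject cell with mean −3% and SD 5.5% (p = 0.10). The cell is empty in all imputed datasets 10% of the time and in at least one 34% of the time.

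**Where the problem is small.** At the 5% threshold the per-stratum chance is 0.00–0.19. In the overall model a 36-subject arm at a 10% rate is empty with probability 0.9^36 = 0.02.

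**The case against.** A reader might infer that secondary objective 1 cannot be delivered. The documents do not support that. The objective asks for responder rates in each subgroup, and SAP 2.7.2.1 already plans a by-stratum responder summary, which is available whether or not a cell is empty. What fails is the set of odds ratios at one of two thresholds.

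A reader might also infer that any empty arm makes all odds ratios infinite, or that nothing can be pooled. An empty active arm sends only its own odds ratio towards 0, with an unbounded SE. Only an empty placebo arm makes the stratum's odds ratios infinite. Software will usually print a number in either case; the trouble is that the number carries no information.

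The frequency does depend on responder rates that the documents do not give. If placebo subjects lose about 3% and low doses are close to maximal (ED50 5 mg), the per-stratum chance falls to 0.11–0.27. That stands, and it is why the full range is shown.

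The analysis is also a subgroup analysis of a secondary endpoint. SAP 2.6 names no key secondary objective, dose selection rests on the primary endpoint, and very large SEs would make the failure visible. This limits the importance of the point but does not supply the missing rule. The summary and the Cochran-Mantel-Haenszel test are additional outputs and are not designated as fallbacks for the odds ratios.

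**Conclusion.** The point holds for the by-stratum 10% responder odds ratios. Following the SAP as written will probably leave at least one of them non-estimable, and no fallback is stated. That likelihood rests on the assumed placebo mean of 0 to −3%, on equal strata with common rates, and on the two Emax shapes; a larger placebo response with near-maximal low doses weakens it. The less frequent but more damaging case is an empty placebo arm, because every contrast in the stratum is then lost. The primary analysis is not affected. This is a cheap improvement to a secondary subgroup analysis and does not bear on the trial's main conclusion.

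**What to change.** In SAP 2.7.2.1, specify Firth-penalised logistic regression for the by-stratum 10% responder models. Pool the log odds ratios and their SEs by Rubin's rule, then back-transform. Add exact intervals to the by-stratum proportions already planned.

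The cost is a sentence or two in the SAP and a model option; no new data are needed. The downside goes beyond slight shrinkage. Where a cell is empty, the odds ratio depends on the penalty and the interval is very wide. In an unadjusted two-arm comparison, where Firth amounts to adding 0.5 to each cell, 0/12 against 5/24 gives (0.5/12.5)/(5.5/19.5) = 0.14 (95% interval 0.007 to 2.8). Likewise 3/12 against an empty placebo of 0/24 gives (3.5/9.5)/(0.5/24.5) = 18 (0.85 to 384). The SAP should therefore say that where a cell is empty the proportions carry the interpretation.

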2.7.2.2 End of study analysis

All analyses will be performed in subjects in the FAS who enter Epoch 4.

A repeated measure ANCOVA model with treatment, visit, pooled center or region, and treatment by visit interaction as fixed-effect factors, BL and BL by visit interaction as covariates, and a common unstructured covariance matrix among visits between treatment will be performed separately for the changes from Week 24 to study end in each efficacy variable (body weight, FPG, HbA1c, SBP, DBP, lipid parameters, hsCRP in \log_{10} transformation, 24-h UGE and waist circumference). The adjusted mean changes from Week 24 to Week 48 within each treatment, the differences in mean changes from Week 24 to Week 48 between the LIK066 and placebo treatments, and their 95% confidence intervals obtained from the above models will be presented. The analysis is based on likelihood method with an assumption of MAR for missing data.

Note that for lipid parameters and hsCRP in \log_{10} transformation, the percent changes (instead of absolute change) from Week 24 to study end will be used as a response variable in the above repeated measure ANCOVA model. For HbA1c and FPG, the repeated measure ANCOVA will be fitted for each stratum (normoglycemic, dysglycemic, and T2DM); and for 24-h UGE, the repeated measure ANCOVA will be fitted for both overall population and for each stratum.

Summaries of absolute values and changes (and/or percent changes for body weight and lipid parameters) from Week 24 by treatment group and visit will be presented for all efficacy variables, for all subjects, and by stratification strata if applicable.

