### **9.5.1.2 End of study analysis**

A repeated measure ANCOVA model with treatment, visit, the stratification factor, pooled center or region, and treatment by visit interaction as fixed-effect factors and BL as a covariate, and a common unstructured covariance matrix among visits between treatment will be performed separately for the changes from Week 24 to study end in each efficacy variable (body weight, FPG, HbA1c, SBP, DBP, lipid parameters, hsCRP, 24-h UGE and waist circumference). The adjusted mean changes from Week 24 to Week 48 within each treatment, the differences in mean changes from Week 24 to Week 48 between the LIK066 and placebo treatments, and their 95 % confidence intervals obtained from the above models will be presented. The analysis is based on likelihood method with an assumption of MAR for missing data.

A similar repeated measure ANCOVA model with additional glycemic stratification factor by treatment interaction and treatment by visit by stratification factor interaction terms will be performed to assess the body weight change from Week 24 to study end across each of the subgroups (normoglycemic subjects, dysglycemic subjects and subjects with T2DM). The p-value for the interaction of treatment by stratification factor at Week 24 will be calculated from this model as well.

Note that for lipid parameters, the percent changes (instead of absolute change) from Week 24 to study end will be used as a response variable in the above repeated measure ANCOVA model.

Summaries of absolute values and changes (and/or percent changes for body weight and lipid parameters) from Week 24 by treatment group and visit will be presented for all efficacy variables, for all subjects and by stratification strata, respectively. Changes from BL will be similarly summarized as well. Figures will be produced to visually show the raw mean changes by visit over entire study period of 48 weeks for each treatment group.

All analyses will be performed in subjects in the FAS who enter Epoch 4.

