2.1 Data analysis general information

Data will be analyzed by Novartis according to the data analysis Section 9 of the study protocol. Important information is given in the following sections and details are provided, as applicable, in Appendix 16.1.9 of the CSR. SAS Version 9.4 or higher will be used to perform all the statistical analyses in the report.

Unless otherwise stated, summary tables/figures/listings will be on all subjects included in the population under consideration.

In general, for continuous data, mean, standard deviation, median, lower quartile, upper quartile, minimum, and maximum will be presented. Categorical data will be presented as frequencies and percentages of patients in each category. For categorical variable summaries, an additional category 'Missing' will be presented if there are missing values for that variable.

If not otherwise specified, p-values will be presented for two-sided hypothesis testing and two-sided confidence intervals will be displayed; the level of significance will be 5% unless otherwise stated.

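### The SAP's end-of-study model drops the glycemic stratum, and its outputs drop the protocol's change-from-baseline summaries and 48-week figure; SAP Section 4 declares none of this

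*SAP*

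**What the plan says.** Protocol 5.3 stratifies randomisation by glycemic status (normoglycemic, dysglycemic, T2DM). Protocol 9.5.1.2 carries that factor into the end-of-study model: "A repeated measure ANCOVA model with treatment, visit, the stratification factor, pooled center or region, and treatment by visit interaction as fixed-effect factors". For the outputs it adds "Changes from BL will be similarly summarized as well" and "Figures will be produced to visually show the raw mean changes by visit over entire study period of 48 weeks for each treatment group".

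SAP 2.7.2.2 gives the model as "A repeated measure ANCOVA model with treatment, visit, pooled center or region, and treatment by visit interaction as fixed-effect factors", with no stratum. Its descriptive outputs are "Summaries of absolute values and changes (and/or percent changes for body weight and lipid parameters) from Week 24 by treatment group and visit"; it mentions neither change from the randomisation baseline nor any figure. Some by-stratum fits remain: "For HbA1c and FPG, the repeated measure ANCOVA will be fitted for each stratum", and "for 24-h UGE, the repeated measure ANCOVA will be fitted for both overall population and for each stratum".

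SAP Section 4, the list of changes to protocol-specified analyses, has one entry, on Week 24 hsCRP. SAP 2.1 meanwhile says that data will be analysed "according to the data analysis Section 9 of the study protocol".

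**The concern.** Two documents in force specify different end-of-study models, and the SAP refers the analyst to the protocol model while writing another. Nothing in either document explains why the Week 24 repeated-measures model should be adjusted for the stratum and the Week 48 model should not. The SAP document history records that the stratification variable was missing from the Section 2.7.2.1 model and was added there; 2.7.2.2 received no such correction.

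The outputs matter for a separate reason. All four qd arms (2.5, 10, 50 and 150 mg) move to 25 mg qd, and all four bid arms (5, 10, 50 and 100 mg total daily dose) move to 35 mg qd. The end-of-study analysis pools each set of four. A change measured from Week 24 then mixes up-dosing and down-dosing and could look like weight regain on a drug that still beats placebo relative to baseline. The summaries and figure in the protocol would show that directly.

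**Working it through.** **Text comparison, protocol 9.5.1.2 against SAP 2.7.2.2**

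| Item | Protocol | SAP 2.7.2.2 | In SAP Section 4? |
|---|---|---|---|
| Stratification factor in overall model | Yes | No | No |
| Change-from-baseline summaries | Yes | No | No |
| Figure of raw means over 48 weeks | Yes | No | No |

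The protocol version does not explain the gap. The SAP refers to the original protocol, but the Amendment 1 change list reports only minor typographical corrections in Section 9. The May 2018 entry in the SAP history covers 2.7.2.2 and announces reduced outputs, but it names subgroup analysis, rescue medication, treatment interruption and exposure categories, and none of these three items.

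**Cost of omitting the stratum**

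Let R² be the share of residual variance that the stratum explains. The documents give no value, so 1%, 5% and 10% are assumed. With allocation balanced within strata, the true variance of a treatment difference excludes the between-stratum part, but the model's standard error includes it.

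- SE ratio = 1/√(1−R²): 1.005, 1.026, 1.054.
- Coverage of the nominal 95% interval = 2Φ(1.96/√(1−R²)) − 1: 95.1%, 95.6% (0.9557), 96.1%.
- Half-width for a pooled active group (36+36+36+72 = 180) against placebo/placebo (36) = 1.96 × SD × √(1/36 + 1/180) = 1.96 × SD × 0.1826. The SDs are the planning values in protocol Table 9-2, used as a stand-in.

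| SD (points) | Stratum omitted | R² = 1% | R² = 5% | R² = 10% |
|---|---|---|---|---|
| 5.5 | 1.97 | 1.96 | 1.92 | 1.87 |
| 6.5 | 2.33 | 2.31 | 2.27 | 2.21 |

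**Why change from Week 24 is not enough by itself**

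In the qd pool, 36+36 = 72 subjects go up (from 2.5 and 10 mg) and 36+72 = 108 go down (from 50 and 150 mg). In the bid pool, 72 go up (from 5 and 10 mg/day) and 108 go down (from 50 and 100 mg/day).

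For the qd pool, take the six candidate shapes in SAP Table 2-3 and scale each to a 5-point maximum weight loss over 0 to 150 mg. Assume effects are at plateau at Weeks 24 and 48 and placebo does not change. For each arm, the Week 24 to 48 change is the effect at 25 mg minus the effect at its Epoch 3 dose. Arms are weighted 36:36:36:72, and negative values favour drug.

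| Shape | Up-dosed | Down-dosed | Pooled Week 24–48 | Week 48 vs baseline |
|---|---|---|---|---|
| Emax, ED50 5 | −1.72 | +0.59 | −0.33 | −4.31 |
| Emax, ED50 50 | −1.51 | +2.22 | +0.73 | −2.22 |
| Sigmoid Emax, ED50 75 | −0.11 | +3.57 | +2.10 | −0.11 |
| Sigmoid Emax, ED50 25 | −1.57 | +1.45 | +0.24 | −3.21 |
| Beta | −1.11 | +2.60 | +1.11 | −1.65 |
| Exponential | −0.37 | +3.21 | +1.78 | −0.48 |

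Worked row (Emax, ED50 50): (72 × −1.51 + 108 × 2.22)/180 = +0.73.

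The pooled change is positive in five of the six shapes, while the Week 48 effect favours drug in all six. No bid figure is given, because those subjects switch to once-daily dosing and the SAP keeps the two regimens' curves separate.

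**The case against.** *The SAP defers to protocol Section 9, so silence is not deletion.* This is arguable for a descriptive table or figure, and SAP 2.1.1 does define a Week 0 baseline for analyses covering both epochs. But no SAP section then specifies a Week 0 to 48 efficacy output. The argument does not reach the model, where the SAP writes out a different list of terms.

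*The May 2018 history entry already discloses the cut.* In part. A general reduction of outputs could be read to cover a table and a figure, but not a main effect in the model. The SAP also logs other changes in its history without listing them in Section 4, so that gap is a general habit and not special to this analysis.

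*The Week 24 parallel is imperfect.* This stands. The main Week 24 repeated-measures model in protocol 9.5.1.1 has no stratum, so there the SAP went beyond the protocol. The history entry shows inconsistency within the SAP, not repair of a protocol departure.

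*The half-widths do not match the model.* Fair as to the illustration. SAP 2.7.2.2 appears to model body weight as absolute change, whereas the SDs are for percent change from baseline. No loss of subjects is applied either: with the 15% effective loss of protocol 9.8, 1.97 and 2.33 become 1.97/√0.85 = 2.13 and 2.33/√0.85 = 2.52. The SE ratios depend on neither.

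*'Precision only' assumes that balance survives.* This also stands. The analysis covers subjects who enter Epoch 4. If entry or dropout depends on stratum, omission could cost more than precision, which is a further reason to include the term.

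*The effect is small and secondary.* Agreed.

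**Conclusion.** The discrepancy is real: three items required by protocol 9.5.1.2 are missing from SAP 2.7.2.2, and none is declared in Section 4. Only secondary end-of-study analyses are affected.

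The missing stratum makes intervals slightly conservative, with standard errors 0.5% to 5.4% too wide for an assumed R² of 1% to 10% and balance within strata. It reaches every end-of-study model not fitted within a stratum: body weight, waist circumference, SBP, DBP, lipids, hsCRP, overall 24-h UGE, and any overall HbA1c or FPG fit. Whether the last two are planned is unclear, because the SAP lists both variables in the general model and then specifies by-stratum fits.

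The missing displays are a loss of presentation. The Week 24 to 48 contrast does answer the objective stated in SAP 1.2, and absolute values by visit remain. The sign reversal is illustrative and not a probability; it is less likely if weight loss is still continuing at Week 24. The change should be made, but it is not critical.

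**What to change.** In SAP 2.7.2.2:

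1. Add the stratification factor (normoglycemic, dysglycemic, T2DM) as a fixed effect in every end-of-study model not fitted within a stratum, and state whether overall HbA1c and FPG fits are planned.
2. Restore the summaries of change from the randomisation baseline and the 48-week raw-mean figure.
3. List in Section 4, with reasons, any departure from protocol 9.5.1.2 that is kept. That list should also carry the added baseline-by-visit term and the end-of-study use of log10 hsCRP, which Section 4 does not mention.

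The cost is one model term (2 degrees of freedom), a table and a figure from data already collected, and a few lines of text.

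Optional, and not the correction of an error: the readable text of both documents plans no modelled change from baseline to Week 48. A supportive model of percent weight change to Week 48 in subjects who enter Epoch 4 could be added, stating that this is a post-randomisation selection. A descriptive weight table by the 10 randomised sequences would use a grouping the SAP already has; most sequences have about 36 subjects or fewer, so it should stay descriptive.
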